### Framework for designing, implementing and testing an adaptability strategy

Our knowledge of the health risks associated with exposures to DDS PM in southern Europe comes mostly from small-scale local or national studies. Despite their limited scope, these investigations have provided sufficient evidence of a real human health risk affecting a large proportion of the EU population. Reversing the unfavourable climate trends that are exacerbating the effect of DDS in the region is a daunting task, and the benefits of global climate change policies will take decades to realize.

At the moment, the EU national competent authorities and mass media in the DDS-exposed regions, during some of the events, issue not-standardised recommendations to the public/vulnerable groups, most commonly advising them to stay indoors, and reduce outdoor activities. To date, no scientific evidence exists on the effectiveness of any of these recommendations in either reducing the exposure to DDS PM or mitigating related health effects. The EU needs to develop evidence-based policies that increase individual, population, and institutional resilience to the growing frequency and intensity of DDS. We propose in three of the most heavily DDS-affected Mediterranean regions (Cyprus, Crete, and Israel) to apply, test and demonstrate the efficacy of patient-specific and population-wide public health interventions to reduce personal exposures to DDS as a means of adaptation.

This study will address a significant knowledge gap in the health effects of personal exposures to desert dust particles, and establish vulnerability assessments in groups such as adults with AF, driven by our findings on the impact of the interventions on exposure, measures of health, and morbidity, thus enabling participant countries to build adaptation strategies and evidencebased policies. During and after the end of the project, this information and knowledge will be used to fine-tune tools for informed decision-making and strategic planning both at national (individual country stakeholders) and cross national levels and will be disseminated to facilitate an exchange of best practices and raise awareness within the population on their vulnerability to DDS pollutants as set out in EU policy priorities.

# 4 STUDY DESIGN

Type of study: Randomized clinical trial (Behavioural Intervention)

Patients with AF will be recruited during DDS outbreaks and will be randomized into three parallel groups to receive:

- a) No intervention for DDS,
- b) Intervention for outdoor exposure reduction, and
- c) Interventions for both outdoor and indoor exposure reduction.

Disease-related adverse health outcomes will be assessed in all the parallel arms of the study.

Previous publications of the MEDEA partners (Achilleos et al, 2014; Gerasopoulos et al, 2006; Krasnov et al, 2014), indicated that 2/3 of each year's DDS events in the Eastern Mediterranean region appear during February-May, with 10-15% of the days during this period being "DDS days". Thus we will perform this public health intervention study during February–May of 2019 and 2020.

Study population and location: Men and women with prior implantation of a dual lead (atrial and ventricular) pacemaker or ICD, will be recruited from the cardiac arrhythmia clinic at the Nicosia General Hospital of Cyprus (n=156) in project years 2018-2019 and 2019-2020. Each patient will have assessment of health outcomes during only one high DDS period.

Duration of the study: A feasibility trial and refinement of protocols and tools will be performed in the high DDS period of 2018. In the fall of 2018 and 2019, MEDEA personnel will start recruitment efforts to detect eligible AF patients for participation in the study during the high DDS periods of February-May 2019 and 2020.

Assessment of health outcomes:

- The occurrence of AF/ventricular arrhythmia episodes will be recorded daily using the already implanted participants' pacemakers or ICD during the 4-month study period. The recorded episodes will be downloaded with interrogation of the pacemaker or ICD during a visit to the Arrhythmia Clinic after the end of the study period.
- Phone interviews every 1 month throughout the high DDS outbreaks season will be carried out. Data collected will include symptoms of fatigue, change in medication use and unscheduled visits to health professionals for heart arrhythmias/episodes.
- Continuous recordings of biological parameters (pulse rate, pulse rate variability and temperature) obtained by wearing smart watch sensors and uploaded on line to the secure e-platform.

# 5 SELECTION AND ENROLLMENT OF PARTICIPANTS

# 5.1 Inclusion Criteria

The inclusion criteria for this panel study will be patients with permanent dual lead (atrial and ventricular) pacemaker or ICD implanted at least two months prior to randomization, with:

- A history of AF or
- Detection of AF in pacemaker/ICD monitoring (continuous recording)

# 5.2 Exclusion Criteria

Exclusion criteria will be:

• Permanent AF

- Patients with reversible causes of AF (eg hyperthyroidism)
- Inability to understand and use study tools (smartphones, software applications)
- Terminal illness
- Active smoking
- Not living at least 5 days per week in the household

# 5.3 Study Enrollment Procedures

Men and women with prior implantation of a dual lead (atrial and ventricular) pacemaker or ICD, will be recruited from the cardiac arrhythmia clinic at Nicosia General Hospital in Cyprus (n=156) in project years 2018-2019 and 2019-2020. Recruitment of participants will be facilitated through the network of physicians at Nicosia General Hospital. In order to facilitate recruitment, relations will be established with the Administrative and Nursing staff of the Clinic and Patients' Association and the details of the project will be explained to them. Patients will be able to ask questions and ask for clarification on all aspects of the program. Each patient participating in the program should complete the necessary consent forms (EKBK03 consent form, see Appendices).

# 6 STUDY INTERVENTIONS

# 6.1 Interventions, Administration, and Duration

Following recruitment, we will randomize participants with a 1:1:1 ratio to three parallel groups to receive:

a) no intervention for DDS

b) intervention for outdoor exposure reduction, by reducing the time spend outdoors and by avoiding physical activity

c) interventions for outdoor (as above) and indoor exposure reduction (by minimizing home ventilation and filtering indoor air).

In the indoor intervention arm of the study, exposure reduction measures will be applied in the patient's household/bedroom settings.

After randomization, and prior to the high DDS season, each eligible participant will complete a questionnaire, providing socio-demographic characteristics, detailed medical and medication history, and will be trained in the tools and procedures to be followed during the monitoring sessions while in the community. The study design offers also the opportunity to assess:

- outdoor exposures to PM,
- indoor exposures to PM and
- related health outcomes in three parallel groups during the same DDS events with and without intervention measures (Figure C8.1).

## Figure C8.1. Study Year 1 (February-May 2019) - 78 patients with AFIB in each study site (Beer Sheba-Israel, Nicosia-Cyprus & Heraklion-Crete) to be randomized to three levels of intervention

### Life+ MEDEA Action C7 Protocol, Version 1.0

## 6.2 Handling of Study Interventions

A bidirectional, patient-centered e-Platform will be created to:

- Communicate promptly forecast alerts to individuals about upcoming DDS events through smartphone applications and text messaging
- Disseminate exposure reduction guidelines

In particular, in the group where there will be intervention for outdoor exposure reduction, the intervention will be carried out by:

- Informing the participant for upcoming desert dust storm episodes.
- Simultaneous transmission of instructions to patient's smartphone to reduce outdoor exposure during the episode (stay indoors, avoid intense physical activity outdoors, avoid competitive sports, avoid unnecessary walks).

In the group where there will be interventions for outdoor and indoor exposure reduction, the intervention will be carried out by:

- Informing the participant for upcoming desert dust storm episodes.
- Simultaneous transmission of instructions to patient's smartphone to reduce a) outdoor exposure during the episode (stay indoors, avoid intense physical activity outdoors, avoid competitive sports, avoid unnecessary walks), and b) indoor, home exposure (closed windows and doors, sealing possible cracks around windows and doors in order to minimize home ventilation, and using an air cleaner in order to filter indoor air).

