#### 8.1 Sample size consideration

There are no studies that evaluated the reduction in AF burden attributed to reduction in exposure to ambient air pollution.

We assume that the mean AF burden in the control group will be 15%+/-15%. We conservatively estimated the expected intervention effect to be 20% of relative reduction in AF burden. This is translated into the reduction of AF burden by mean of 43 minutes per 24 hours.

Group sample sizes of 108 and 216 achieve 81% power to show a difference in means when there is a difference of -3.0 between the null hypothesis mean difference of 0.0 and the actual mean difference of 3.0 at the 0.05 significance level (alpha) using a two-sided Mann-Whitney-Wilcoxon Test. These results are based on 2000 Monte Carlo samples from the null distributions: WeibullMS(15 15) and WeibullMS(15 15), and the alternative distributions: WeibullMS(15 15) and WeibullMS(15 15).

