### Hierarchical model

Generalized Linear Model will be used to fit a Poisson regression of daily AF episodes against temporal variables and DDS data based in hierarchical model. Data model with random effect include repeated episodes of AF in each patien, the intervention groups and the 3 sites of the research. Date model with fixed effect include DDS event during the period of the study.

Analysis will be performed using R Project for Statistical Computing version 3.0 or higher and IBM SPSS software version 23 or higher.

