Mitigating the Health Effects of Desert Dust Storms Using Exposure-Reduction Approaches (MEDEA) project

Assessment of health outcomes in children with asthma (ACTION C.7) and in adults with atrial fibrillation (ACTION C.8) during DDS events (with vs without intervention measures)

Public Health Intervention Study

Statistical Analysis Plan

(April 2018)

1. Sample Size Determination and Power Calculations

Sample size calculations for the panel study of asthmatic children

Sample size calculations are based on expected changes in asthma symptoms measured by asthma control test (ACT), which is our primary health outcome. Childhood ACT has seven items and provides a score ranging from 0 (poorest asthma control) to 27 (optimal asthma control). A cut-off point of 19 indicates uncontrolled asthma. Previous studies have shown that a minimally meaningful change in the ACT score is ranging from 2 to 3 points (Voorend-van Bergen et al, 2014). To detect a statistically significant difference of 3 points, the minimum sample size needed in each of the 3 groups is 100 participants. This sample size calculation is assuming a level of 0.05 and a power of at least 80% to detect this difference between the comparison groups.

Sample size calculations for the panel study of atrial fibrillation (AF) patients

There are no studies that evaluated the reduction in AF burden attributed to reduction in exposure to ambient air pollution.

We assume that the mean AF burden in the control group will be 15%+/-15%. We conservatively estimated the expected intervention effect to be 20% of relative reduction in AF burden. This is translated into the reduction of AF burden by mean of 43 minutes per 24 hours. Group sample sizes of 108 and 216 achieve 81% power to show a difference in means when there is a difference of -3.0 between the null hypothesis mean difference of 0.0 and the actual mean difference of 3.0 at the 0.05 significance level (alpha) using a two-sided Mann-Whitney-Wilcoxon Test. These results are based on 2000 Monte Carlo samples from the null distributions: WeibullMS(15 15) and WeibullMS(15 15), and the alternative distributions: WeibullMS(15 15) and WeibullMS(12 15).

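### Patients are enrolled by site and season, but no named two-group test of AF burden uses either factor, and the one AF model naming site treats arm and site as random: a cheap gain in precision is left unused

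*Protocol*

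**What the plan says.** **Enrolment.** The Protocol Summary (Study Population) plans 156 patients at each of Beer Sheba, Heraklion and Nicosia, 468 in all, with 324 left to analyse. The Figure C8.1 caption puts "78 patients with AFIB in each study site" into the February–May 2019 season, to be randomised to the three levels of intervention. Protocol section 4 says each patient is assessed in one high-dust season only, so every patient belongs to one site and one season.

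**Randomisation.** Protocol 7.2.2 gives 1:1:1 allocation by random number generation in PASS 14. It names no strata and no blocks.

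**Tests for burden.** The primary contrast is the two intervention groups combined against control (Protocol 2.1). The power statement in both documents is made "using a two-sided Mann-Whitney-Wilcoxon Test". The analysis sections (Protocol 8.2.2; SAP, Univariate analysis) list t-tests and repeated-measures ANOVA first, with rank tests if parametric assumptions fail. None of these tests has a site or season term.

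**Models.** The Hierarchical model paragraphs describe a Poisson regression of daily AF episodes whose random effects cover repeated episodes in each patient, "the intervention groups and the 3 sites of the research". Dust events are the fixed effect, and unspecified temporal variables are mentioned. The SAP also says the mixed-model formulas from its asthma section will be applied to AF outcomes. Those have spatial and temporal predictors but no named site or year term.

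**The concern.** Dust exposure, climate and device clinics may differ between three countries and two years, and AF burden may differ with them. A test that ranks all patients together counts such differences as noise. If arms happen to be balanced within site and season, that noise is not in the treatment comparison at all. The pooled test's reference variance is then too large and the test rejects too rarely.

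The Poisson model does not fill the gap. Its outcome is episode count, not the time percentage that defines burden. With arm as a random effect, the model estimates a variance among three arms and does not directly estimate the intervention-minus-control contrast. With site as a random effect, it rests on a variance estimated from three levels. Study year is not named in any AF analysis.

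What is at stake is power and a clearly stated treatment estimate, not protection against false positives.

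**Working it through.** **Inputs from the documents.** Test: "at the 0.05 significance level (alpha) using a two-sided Mann-Whitney-Wilcoxon Test". Sizes: "Group sample sizes of 108 and 216 achieve 81% power to show a difference in means". Control burden: "We assume that the mean AF burden in the control group will be 15%+/-15" per cent. Effect: 20% relative, so 15 × 0.20 = 3 points, giving a mean of 12. The SAP alternative is Weibull with mean 15, SD 15 against mean 12, SD 15. Solving for shape and scale gives 1.000 and 15.00 for control, and 0.806 and 10.65 for intervention.

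**Stated power.** At 108/216 with the SAP inputs, 20,000 simulated trials give 76.4%, not 81%. The sponsor's 2,000 samples carry an error of 1.96 × √(0.764 × 0.236 / 2000) = 1.9 points, which does not cover the gap. An equal split, 162/162, gives 80.7%. The Protocol version, with both alternatives at mean 15 and SD 15, has no effect in it and returns 5%. These are separate matters. Here they mean only that the baseline is about 76%.

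**Cells.** 156 − 78 = 78 per site remain for 2020, so there are 3 sites × 2 seasons = 6 cells. Analysed: 324 / 6 = 54 per cell, that is 18 control and 36 intervention if arms are balanced within cells.

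**Tests.** With W the rank sum of the intervention patients:
- Pooled: Z = (W − n₁(N+1)/2) / √(n₁n₀(N+1)/12) = (W − 216 × 325/2) / √(216 × 108 × 325/12) = (W − 35,100) / 794.9.
- Van Elteren: Z = Σ w(W_c − n₁c(N_c+1)/2) / √(Σ w² n₁c n₀c(N_c+1)/12), summed over cells, with w = 1/(N_c+1) = 1/55.

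**Assumption.** The documents give no site-season spread in burden. Each cell's burden is multiplied by a factor with average 1, and the factors are varied.

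*Multipliers, arms balanced within cells, 6,000 trials:*

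| Multipliers | Control cell means, % | Size %, pooled / stratified | Power %, pooled / stratified |
|---|---|---|---|
| none | 15 | – | 77.1 / 76.0 |
| 0.6–1.4 | 9 to 21 | 4.4 / 5.1 | 75.0 / 75.9 |
| 0.35–1.65 | 5.3 to 24.8 | 3.0 / 5.0 | 72.2 / 76.5 |

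Under unrestricted allocation at 0.35–1.65, the pooled size is 4.9% and power is 70% pooled against 75% stratified. So the power difference does not need stratified randomisation.

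*Log-normal spread, SAP SDs within each cell, 10,000 trials, balanced / unrestricted allocation:*

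| Log-SD | Control cell means, % | Pooled size % | Stratified size % | Pooled power % | Stratified power % |
|---|---|---|---|---|---|
| 0 | 15 | 5.0 / 4.9 | 4.8 / 4.9 | 76.3 / 77.3 | 75.6 / 75.9 |
| 0.2 | 10.8–20.0 | 4.6 / 4.8 | 5.0 / 5.1 | 74.9 / 75.6 | 74.8 / 74.8 |
| 0.4 | 7.5–25.7 | 3.7 / 4.9 | 5.1 / 5.2 | 73.4 / 72.8 | 75.7 / 75.3 |
| 0.6 | 5.0–31.8 | 2.7 / 5.0 | 5.1 / 4.8 | 69.8 / 69.6 | 75.7 / 75.8 |
| 0.8 | 3.2–38.0 | 1.5 / 5.4 | 4.8 / 5.2 | 65.6 / 63.2 | 75.8 / 75.4 |

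Simulation error is about 1.96 × √(0.05 × 0.95/10,000) = 0.4 points for size and 1.96 × √(0.76 × 0.24/10,000) = 0.8 points for power.

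*Overall SD held at 15, so that spread between cells replaces spread within them.* Power, pooled against stratified:
- Log-SD 0.2: 78.7 against 78.6 (balanced), 77.6 against 77.3 (unrestricted).
- Log-SD 0.4: 81.0 against 83.1, and 80.8 against 83.7.
- Log-SD 0.6: 86.5 against 91.6, and 82.8 against 91.7.

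**The case against.** The strongest reply is that nothing in the plan is invalid and the gain may be nil. Most of this stands.

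- **Blocks.** A reader might infer from the Figure C8.1 caption that arms are balanced within six site-season blocks, so that the analysis departs from the randomisation. The caption shows enrolment by site in one year, and Protocol 7.2.2 names no strata or blocks. The conservative sizes above apply only if arms are in fact balanced within cells.
- **Error rate.** A reader might infer that the test's error rate is wrong in the harmful direction. It is not. The pooled size stays near 5% under unrestricted allocation and falls below 5% under balance. No setting showed inflation beyond simulation error.
- **Primary test.** A reader might take the rank test as the designated primary analysis. It is the power-calculation test and a fallback. No test is expressly assigned to the burden contrast. The alternatives listed beside it omit site and season too.
- **Size of the loss.** The largest gains need large differences. Multipliers of 0.35 to 1.65 are a 1.65/0.35 = 4.7-fold range in mean burden and, if evenly spaced, raise the overall control SD from 15 to 15 × √(2 × 1.197 − 1) = 17.7. The documents put only 10–15% of season days as dust days and do not support a difference of that order.
- **The mixed model.** Its weather, land-use and similar predictors could absorb part of the site and season differences. That is possible, but it names neither factor and is not tied to the burden contrast.

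What remains is that site and season are known features of enrolment, no named burden test uses them, and using them costs almost nothing.

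**Conclusion.** The point holds as a precision improvement, not as a validity fault. No named two-group test for AF burden accounts for site or season. The Poisson model that names site has a different outcome and treats arm and three sites as random, so it does not directly estimate the treatment contrast.

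The size is conditional on an assumed spread:
- no spread: the pooled test is about 1 point better;
- multipliers 0.6–1.4: about 1 point lost;
- multipliers 0.35–1.65: 4 to 5 points lost.

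Larger losses, up to about 12 points (75.4 − 63.2 at log-SD 0.8), appear only at spreads that nothing in the documents suggests. That power is certainly lost is therefore a further reading the documents do not support. The result rests on the SAP's Weibull distributions, equal cells of 54 and a baseline of about 76% power. The trade is lopsided: about 1 point at risk against several to gain, in a trial with little power to spare.

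**What to change.** 1. In Protocol 8.2 and the SAP, compare AF burden between the combined intervention groups and control with a Wilcoxon test stratified by site and season (van Elteren), or with a model that has site and season as fixed effects. Name this as the analysis of the burden contrast.
2. In the Poisson model of daily episodes, make arm, site and season fixed effects and keep patient as the random effect.
3. State in Protocol 7.2.2 whether allocation is stratified or blocked by site and season, since this decides whether a pooled test would be nominal or conservative.

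The cost is a wording change, with no extra data or patients. The downside is about 1 point of power if sites and seasons turn out not to differ.

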## 6.3 Adherence Assessment

The compliance to exposure-reduction guidelines will be monitored with the use of remote sensors. The intervention for outdoor exposure reduction, (by reducing the time spend outdoors and by avoiding physical activity) will be assessed with the use of smart wristwatches that will have global position system (GPS) and accelerometer. The intervention for indoor exposure reduction (by minimizing home ventilation and by filtering indoor air) will be assessed with the use of particle samplers that will be placed outside and inside houses.

# 7 STUDY PROCEDURES

# 7.1 Schedule of Evaluations

Assessment	Baseline	Every 1 month ± 3 days.	4 months ± 30 days
Informed Consent Form	X		
Inclusion/Exclusion Criteria	Х		
Demographics	X	X	
Medical History	X	X	
House assessment		X	
Current Medications	Х	X	X
Intervention Discontinuation		X	X
Tel Questionnaire		X	
Daily recordings of AF/ventricular arrhythmia episodes			X
Continuous recordings of biological parameters (pulse rate, pulse rate variability, temperature)		x	X
Adverse Events		X	X

#### 7.2 Description of Evaluations

#### 7.2.1 Screening and Enrollment Evaluation

These evaluations occur to determine if the candidate is eligible for the study.

#### **Consenting Procedure**

Before any screening procedure is performed, informed consent must be obtained. There will be one consenting process that describes the study procedure. Patients will be asked by the study personnel to read their consent forms, and will be given the opportunity to ask any clarification question for the purposes of the study and their participation. Following a discussion with the patients, they will be asked to give their signed approval. The explanations given to the patients will be in comprehensible non-technical terminology.

#### Screening and Enrollment

In fall 2018 and 2019, screening of patients attending the cardiac arrhythmia clinic will be performed with the help of the network of physicians at Nicosia General Hospital. During screening, each patient will have at the clinic demographic, medical, medication and symptom survey. The enrollment date is the day the participant has met all the screening criteria (both inclusion and exclusion criteria) and signs the informed consent form.

